6.5.2 Vital signs

Vital signs will be collected as described in Table 6-1. These will include supine and standing heart rate and systolic and diastolic blood pressures. After the patient has been supine for 5 minutes, systolic and diastolic blood pressure will be measured 3 times using an automated validated device (e.g., OMRON) with an appropriately sized cuff. The repeat measurements will be made at 1- to 2-minute intervals, and the mean of the 3 measurements will be used. In case the cuff sizes available are not large enough for the patient's arm circumference, a sphygmomanometer with an appropriately sized cuff may be used. Heart rate and blood pressure will then be measured in the same manner with the patient in the standing position. A sudden, significant fall in blood pressure (>20 mm Hg systolic or >10 mm Hg diastolic) between 2 and 5 minutes after standing from the supine position will be defined as orthostatic hypotension.

Body weight will be measured as described in Table 6-1. Body temperature will be measured only at Screening, Visit 7/EOT, and at follow-up.

Clinically notable vital signs are defined in Appendix 1.

6.5.3 Laboratory evaluations

Routine blood samples will be collected as described in Table 6-1 and Table 6-2 and analyzed by the central laboratory. Blood samples taken at the screening visit are to be in the fasting state. Blood samples taken at subsequent visits are recommended to be in the fasting state. Details regarding collection of samples, shipment of samples, reporting of results, laboratory reference ranges, and alerting abnormal values will be supplied to the site before site initiation in a study laboratory manual. The results of the analysis will be made available to each site by the central laboratory, at the earliest, 48 hours after receipt of the samples by the central laboratory.

Investigators will be asked to comment on those abnormalities on the respective laboratory result page, including a notation of the clinical significance of each abnormal finding in the patient's source documents. The laboratory sheets will be filed with the patient's source documents. Abnormal laboratory values should not be recorded on the AE eCRF; however,

any diagnoses (or signs or symptoms if a diagnosis is not possible) associated with the abnormal findings should be recorded on the AE eCRF.

Clinically notable laboratory findings are defined in Appendix 1.

6.5.3.1 Hematology

Hematology parameter blood samples will be collected as described in Table 6-1 and will include: red blood cell count, total and differential WBC count (basophils, eosinophils, lymphocytes, monocytes, and neutrophils), platelet count, hemoglobin, hematocrit, mean corpuscular volume, mean corpuscular hemoglobin, mean corpuscular hemoglobin concentration, and red blood cell morphology. In a subset of patients CD4+, CD8+, Th17, Treg, and other T-lymphocyte subsets will be determined.

For study blinding purposes (of fingolimod arms) only the absolute counts for eosinophils, basophils, and monocytes will be communicated to sites by the central laboratory. The absolute total WBC, neutrophil, and lymphocyte counts will be measured at each visit by the central laboratory and will be blinded from the sponsor and the Investigator and will only be communicated to the site in case of a notable abnormality as defined in Appendix 1 and as per guidance in Appendix 3.

6.5.3.2 Clinical chemistry and blood serology

Blood samples will be collected as described in Table 6-1 and will include the following parameters: sodium, potassium, chloride, bicarbonate, calcium, magnesium, phosphate, blood urea nitrogen, uric acid, random glucose, albumin, AP, creatinine, ALT, AST, GGT, amylase, total bilirubin, conjugated bilirubin, HbA1c, total cholesterol, triglycerides, high-density lipoprotein, and low-density lipoprotein. Abnormal laboratory parameters inconsistent with clinical presentation of MS or suspicious of underlying medical condition should be repeated for accuracy.

If an increase of amylase above the clinically notable value (\geq 300 U/L) is observed at any postrandomization visit, lipase should be tested to determine the origin of elevated amylase (pancreatic versus extra-pancreatic).

Serology testing will also be performed in all patients at Screening to determine the patient's immune status with respect to the following viruses:

- Herpes simplex virus-1 (HSV-1)
- Herpes simplex virus-2 (HSV-2)
- Rubeola (Measles)
- Human immunodeficiency antibodies

Patients without acceptable evidence of immunity against VZV (per Appendix 3) at Screening will be excluded from the study. Patients testing positive for HIV are excluded from the study.

Patients who are negative for HSV-1 immunoglobulin G (IgG), HSV-2 IgG or rubeola IgG antibodies should be informed of their status and be instructed to promptly report any exposure to these viruses e.g., to a person with cold sores, herpes genitalis, or measles, respectively. In case of exposure, early treatment with appropriate antiviral drugs and/or immunoglobulin should be considered in consultation with a local infectious disease expert.

A positive IgG antibody result does not indicate active infection per se, but only evidence of prior exposure to viral antigens through past infection or vaccination. Patients with prior infection may be at risk of viral reactivation (e.g., cold sores, genital ulcers or shingles) and should be instructed to inform the investigator of any signs or symptoms suggestive of these conditions, so that prompt treatment may be initiated.

If a patient experiences symptoms of a new ischemic or thrombotic AE, the following additional laboratory assessments should be performed: prothrombin time/partial thromboplastin time, homocysteine, activated protein C, lupus anticoagulant, antiphospholipid antibody, protein C, protein S, fibrinogen, and antithrombin III.

A serum pregnancy test will be conducted at Screening on all females, regardless of child-bearing potential.

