5.5.8 Concomitant treatment

All concomitant medications taken within 30 days before Screening (Visit 1) and during the study must be recorded. Both the start date and the end date for each medication should be captured on the prior medications/significant nondrug therapies eCRF, the previous MS treatment eCRF, the concomitant medications/significant nondrug therapies eCRF, and the steroid treatment of MS relapses eCRF.

Patients taking dimethyl fumarate, glatiramer acetate, or IFN beta before study entry may continue to take this medication up to the last day before randomization. These patients will be randomly assigned to and start study drug on the day of their next scheduled dose.

A standard short course of corticosteroids (methylprednisolone IV) is allowed for treatment of relapses (Section 5.5.7). Treatment with topical corticosteroids in the eyes, ears, or nose, on the skin or through inhalation, is also allowed, if the potential systemic absorption of the corticosteroid component due to that treatment can be regarded as negligible and the condition being treated does not warrant study discontinuation per protocol. If a course of systemic corticosteroid treatment is required for treatment of uveitis, this is also acceptable.

The medications allowed for the treatment of adverse reactions and relapses are not considered study supplies and, therefore, need to be supplied by the study site.

Medications for the symptomatic treatment of MS such as baclofen, fampridine, methylphenidate, or modafinil are acceptable. As far as possible, every effort should be made to keep the dosages stable from Screening through EOT.

The investigator should instruct the patient to notify the study site about any new medications that they take after the start of the study drug. All medications and significant nondrug therapies (including physical therapy and blood transfusions) administered after the patient starts treatment with study drug must be recorded on the concomitant medications/significant nondrug therapies eCRF and steroid therapies eCRF.

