5.5.9 Prohibited treatment

Use of the following treatments is NOT allowed after randomization:

- Immunosuppressive medication (e.g., cyclosporine, azathioprine, methotrexate, cyclophosphamide, mitoxantrone, cladribine)
- Other concomitant medications: immunoglobulins, monoclonal antibodies (including natalizumab), IFN beta, adrenocorticotropic hormone, other disease-modifying medications approved for MS including those approved subsequent to the start of this study

The administration of any live or live-attenuated vaccine (including for measles) is prohibited while patients are receiving fingolimod and for 8 weeks after fingolimod discontinuation.

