To verify a history of VZV, health care providers should inquire about:

- An epidemiologic link to another typical VZV case or to a laboratory confirmed case,
- Evidence of laboratory confirmation, if testing was performed at the time of acute disease

The VZV vaccination of antibody-negative patients should be considered prior to commencing treatment with fingolimod, following which initiation of study drug should be postponed for at least 1 month to allow full effect of vaccination to occur.

Serology testing for antibody status of HSV-1 and HSV-2 and rubeola (measles) is performed at screening to profile infection risk in study patients. The investigator should inform the patients of their immune status based on these serology results and of the potential risks of primary infections or viral reactivation while taking fingolimod.

A positive IgG antibody test result does not indicate active infection per se, but only evidence of exposure to viral antigens via past infection or vaccination. These patients may however, be at risk for viral reactivation, which may manifest as:

- VZV virus IgG positive: Shingles
- HSV-1 IgG positive: Cold sores
- HSV-2 IgG positive: Herpes genitalis

The investigator should instruct the patient to be alert to and report any symptoms or signs suggestive of cold sores, genital ulcers or shingles, so that appropriate anti-viral treatment can be initiated in consultation with a local infectious disease expert (if needed).

A negative IgG antibody test result for HSV-1, HSV-2, and rubeola places patients at risk for more severe and atypical manifestations of primary infection in the event they are exposed to these viruses while they are immunosuppressed (taking study drug and/or corticosteroids).

Patients who are negative for HSV-1 IgG, HSV-2 IgG and rubeola antibodies should be instructed to promptly report any exposure to these viruses i.e. to a person with cold sores, herpes genitalis, respectively. In case of exposure, early treatment with appropriate antiviral drugs should be considered in consultation with a local infectious diseases expert.

It is also important to ask the patient receiving fingolimod to report if they are exposed to anyone who has recently received a live or live attenuated vaccine and manifested a skin rash after the vaccination so that it can be decided, in consultation with an infectious disease expert, if antiviral therapy is warranted.

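### Protocol Section 6.5.3.2 offers immunoglobulin after viral exposure, Section 5.5.9 prohibits it after randomisation without exception, and Appendix 3 leaves it out; the three must be reconciled

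*Protocol*

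**What the plan says.** Protocol Section 6.5.3.2 requires serology for HSV-1, HSV-2 and rubeola at screening. It continues: "Patients who are negative for HSV-1 immunoglobulin G (IgG), HSV-2 IgG or rubeola IgG antibodies should be informed of their status". These patients are told to report exposure promptly, with cold sores, genital herpes and measles given as examples. If exposure occurs, "early treatment with appropriate antiviral drugs and/or immunoglobulin should be considered in consultation with a local infectious disease expert".

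Protocol Section 5.5.9 opens with "Use of the following treatments is NOT allowed after randomization". Its second bullet reads, in part, "Other concomitant medications: immunoglobulins, monoclonal antibodies (including natalizumab), IFN beta". It limits the ban on immunoglobulins by neither route nor indication, and states no end to it.

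Appendix 3, in its guidance on infections, addresses the same seronegative patients. There, "early treatment with appropriate antiviral drugs should be considered in consultation with a local infectious diseases expert", and immunoglobulin is not named. Rubeola is among the viruses listed, but the examples of exposure are given as "i.e. to a person with cold sores, herpes genitalis, respectively", so the third example, contact with measles, is missing.

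**The concern.** One section offers as an option a product that another section bars outright, and a third section on the same situation does not mention it. This concerns a safety instruction. Appendix 3 warns that a seronegative patient who meets one of these viruses while immunosuppressed may have a more serious or unusual first infection, and both 6.5.3.2 and Appendix 3 call for early treatment.

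Two things are at stake. First, two sites facing the same exposure may act differently according to which section they read. Second, a patient treated in a way that 6.5.3.2 allows has also received a drug that 5.5.9 prohibits, so the deviation record would partly reflect the conflict in the text rather than the conduct of the site.

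**Working it through.** No arithmetic applies. The check sets the passages side by side and then tests whether anything else in the protocol resolves them.

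| Question | Section 6.5.3.2 | Section 5.5.9 | Appendix 3 |
|---|---|---|---|
| Who | Negative for HSV-1, HSV-2 or rubeola IgG | All patients from randomisation | Negative for HSV-1, HSV-2 and rubeola |
| Antiviral after exposure | To be considered | Not listed as prohibited | To be considered |
| Immunoglobulin after exposure | To be considered, alone or with an antiviral | Prohibited, no exception | Not mentioned |
| Measles contact as an example | Yes | Not applicable | Missing |

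**Do the passages overlap in time?** Yes. Section 6.5.3.2 sets no time limit on the exposure it covers, and Appendix 3 places the risk in the period when the patient is taking study drug or corticosteroids. That period lies after randomisation, where 5.5.9 applies.

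**What happens under each choice?**

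1. The site considers both options and gives only an antiviral. It complies with 6.5.3.2, 5.5.9 and Appendix 3.
2. The site gives immunoglobulin, alone or with an antiviral. It has used an option offered in 6.5.3.2 and breached 5.5.9.
3. The site works from Appendix 3 alone. It does not see immunoglobulin as an option, and it has no measles example to give to a rubeola-negative patient.

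The direct conflict is therefore between 6.5.3.2 and 5.5.9, and it appears only in the second case. The gap in Appendix 3 is an omission.

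**Is there an exception elsewhere?** None was found. Section 5.5.8 shows that the protocol writes exceptions out when it means them: "If a course of systemic corticosteroid treatment is required for treatment of uveitis, this is also acceptable". It has no such line for immunoglobulin.

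**Do other provisions remove the conflict?**

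- Section 11.1 expects the investigator to act at once where a patient's safety requires it, deviation or not. The sponsor is then notified, and the ethics board is informed within 10 working days. The treatment can go ahead, but it remains a deviation.
- Section 5.5.6 lists an emergency or unplanned admission involving prohibited drugs among the possible reasons to interrupt study drug. It does not lift the prohibition, which runs from randomisation and is not tied to time on drug. Treatment after exposure also need not involve an emergency or an admission.
- Section 11 rules out authorised deviations, so a site cannot clear the matter beforehand by asking the sponsor to approve one.

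**Does it reach the analysis?** SAP Section 3.3 assigns severity codes to deviations, but the criteria sit in a separate document (VAP Module 3). Whether this use would count as a major deviation cannot be read from the protocol or SAP.

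**The case against.** The strongest case on the other side is that the protocol already copes. Section 6.5.3.2 asks only that the options be considered, and it joins them with and/or, so no site is forced to give immunoglobulin. Section 11.1 supplies the route for urgent cases and needs no prior approval. Section 5.5.6 anticipates prohibited drugs in an emergency, and Appendix 3 leaves the treatment of infections to the investigator's judgement. Section 5.5.10 adds that violations should not lead to withdrawal unless they point to a significant safety risk.

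All of this stands as an answer to a stronger reading. A reader might infer that a site cannot follow the protocol after an exposure, or that the rule against authorised deviations leaves treatment blocked. The documents support neither inference. None of these provisions, however, makes 6.5.3.2 and 5.5.9 agree or stops the use of immunoglobulin from being a deviation.

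A second argument is that 5.5.9 is aimed at immunoglobulin as an MS treatment. The same bullet names natalizumab, IFN beta and other disease-modifying drugs, and the amendment rationale describes exclusion criterion 3, which includes IV immunoglobulin, as concerning earlier MS treatments. That intention is plausible, but the section does not state it, and a monitor applying the text would have no ground for reading it in.

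Third, Appendix 3 does not forbid immunoglobulin, and it does cover measles, because it names rubeola and asks for any exposure to be reported. This is correct. A reader might take the missing example to mean that measles contact need not be reported, but the sentence does not say that. It is a drafting slip that should be corrected in the same revision.

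**Conclusion.** The inconsistency is real, and nothing in the protocol resolves it. Its consequence is limited: treatment is not blocked, but a site that gives the immunoglobulin offered in 6.5.3.2 departs from 5.5.9, and practice and deviation coding may differ between sites.

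Its size cannot be given. The documents state neither the share of seronegative patients nor how often exposure is expected. A reader might infer that patients would be lost from the per-protocol set or that the relapse-rate comparison would be affected. The documents do not support either, since the coding criteria are not in them and the per-protocol set serves only supportive analyses. No effect on the primary analysis is claimed.

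The conclusion assumes that 5.5.9 is applied as written, without an unstated limit to MS use.

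**What to change.** The sponsor should reconcile Sections 5.5.9 and 6.5.3.2 and Appendix 3 so that they state one position on immunoglobulin after viral exposure and name the same exposures, including measles. Which clinical rule applies is for the sponsor to decide, and this review proposes none.

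The handling of protocol deviations should then follow the reconciled text, whichever way it is settled. It should not be fixed in advance, because any exemption would presuppose that immunoglobulin is permitted. No new data collection is needed, since Section 5.5.8 already requires start and end dates for every concomitant medication.

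The cost is wording in three places, a check of the deviation criteria against it, and a letter to sites. The wording change goes through the normal amendment route.

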6.5.3.3 Urinalysis

Urinalysis will be performed as indicated in Table 6-1 and Table 6-2. The following parameters will be analyzed: leukocytes, specific gravity, bilirubin, blood, glucose, ketones, pH, protein, and urobilinogen.

If a patient experiences edema or significant weight gain (Appendix 1), urinalysis by dipstick for proteinuria will be performed. If dipstick urinalysis detects proteinuria, urinalysis should be repeated. If proteinuria is confirmed upon repeat testing, the protein/creatinine ratio should be determined in a spot urine sample. In case of abnormal spot urine protein/creatinine ratio, the patient should be referred to a nephrologist for further evaluation and assessments, including possible 24-hour urine collection.

6.5.4 Electrocardiogram

Standard 12-lead ECGs will be collected as described in Table 6-1. Digital ECG devices will be provided to each clinical site by the central ECG reader for the duration of the study. The screening ECG report from the central reader must be available to confirm patient eligibility before randomization. A 12-lead ECG will be performed at Visit 2 before study drug administration for patients receiving fingolimod and patients receiving glatiramer acetate and 6 hours after the study drug administration, for patients receiving fingolimod only.

See Section 5.5.5 for guidelines for monitoring patients taking their first dose of fingolimod who had a prolonged QTc interval (>450 msec males, >470 msec females) before dosing or during a 6-hour observation period, or at additional risk for QT prolongation (e.g., hypokalemia, hypomagnesemia, congenital long-QT syndrome), or on concurrent therapy with QT-prolonging drugs with a known risk of torsades de pointes.

Detailed instructions describing the process for recording and transmission of the ECGs will be outlined in the study-specific manual and provided to the site before the start of the study. Paper ECGs will be printed, photocopied to preserve the ink if necessary, and kept at the site as source documentation.

Interpretation of the tracing must be made by a qualified physician. Each ECG tracing should be labeled with the study number, patient initials, patient number, date, and kept in the source documents at the study site. Only clinically significant abnormalities should be reported as medical history/current medical conditions or AEs on the eCRF. Clinically significant findings must be discussed with the Medical Monitor before enrolling the patient in the study.

6.5.5 Ophthalmologic examinations and optical coherence tomography

An ophthalmic examination will be performed to screen for macular edema as described in Table 6-1 and Table 6-2 for patients that discontinued study drug. An optical coherence tomography (OCT) and fluorescein angiography (FA) will be done only if needed to confirm macular edema. If there is a suspicion of macular edema at Screening, an OCT and FA should be performed to confirm the diagnosis. If the diagnosis is confirmed, the patient should be deemed a screening failure and should not be randomly assigned.

Patients with a history of or newly diagnosed uveitis after initiation of study drug may require more frequent ophthalmic evaluations. Refer to the Guidance for Ophthalmic Monitoring (Appendix 4) for details on monitoring of patients with uveitis during the study.

Study drug must be discontinued in any patient who has a diagnosis of macular edema confirmed by OCT and FA.

Patients with a diagnosis of macular edema must be followed up monthly and more frequently if needed based on the ophthalmologist's judgment. Further ophthalmologic evaluations will be conducted until such time as resolution is confirmed or no further improvement is expected by the ophthalmologist (based on a follow-up period of not less than 3 months). If the patient does not show definite signs of improvement on examination by specialized testing (e.g., OCT) 6 to 8 weeks after discontinuation of study drug, then therapy for macular edema in conjunction with an ophthalmologist experienced in the management of this condition should be initiated.

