Investigational drug	The study drug whose properties are being tested in the study; this definition is consistent with US CFR 21 Section 312.3 and is synonymous with "investigational new drug."
Medication number	A unique identifier on the label of each study drug package in studies that dispense study drug using an IVR system
Patient number	A number assigned to each patient who enrolls in the study. When combined with the center number, a unique identifier is created for each patient in the study.
Period	A minor subdivision of the study timeline; divides phases into smaller functional segments such as screening, baseline, titration, washout, etc.
Premature patient withdrawal	Point/time when the patient exits from the study before the planned completion of all study drug administration and assessments; at this time all study drug administration is discontinued and no further assessments are planned
Randomization number	A unique identifier assigned to each randomly assigned patient, corresponding to a specific treatment arm assignment
Stop study participation	Point/time at which the patient came in for a final evaluation visit or when study drug was discontinued whichever is later
Study drug	Any drug administered to the patient as part of the required study procedures; includes investigational drug and any control drugs
Study drug discontinuation	Point/time when patient permanently stops taking study drug for any reason; may or may not also be the point/time of premature patient withdrawal
Variable	Information used in the data analysis; derived directly or indirectly from data collected using specified assessments at specified timepoints

Amendment 02

Amendment rationale

This amendment implements changes to the CFTY720D2312 protocol amendment 1 (dated 20-Nov-2012) to address recommendations and requests received from the United States (US) Food and Drug Administration (FDA).

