First-dose monitoring		X						
Urinalysis	Х	X	Х	Χ	Χ	Χ	Х	Х
Study drug dispensation		X	Х	Χ	Χ	Χ		
Study drug accountability			Χ	Χ	Х	Х	Х	
Magnetic resonance imaging	Х						Х	
EDSS	Х						Х	Х
MS relapse ^g	X	X	Χ	Χ	Χ	Χ	Χ	Χ
TSQM	X				Χ		Х	
C-SSRS	Х	X		Χ	Χ	Χ	Х	Χ
Adverse events/SAEs	X	X	Χ	Χ	Χ	Χ	X	Χ
Study completion form							X	

Abbreviations: C-SSRS=Columbia-Suicide Severity Rating Scale; ECG=electrocardiogram; EDSS=expanded disability status scale; EOT=end of treatment; FU=follow-up; HSV=herpes simplex virus; MS=multiple sclerosis;

; SAE=serious adverse event;

TSQM=treatment satisfaction questionnaire for medication.

- a. Follow-up will occur 3 months (12 weeks) after the last dose of study drug for all patients.
- b. The ophthalmology examination will include eye history, visual acuity, dilated ophthalmoscopy, and any procedures necessary to assess macular edema. Optical coherence tomography and fluorescein angiography will be done only if needed to confirm macular edema.
- c. Body temperature is collected only at Screening, Visit 7/EOT, and at the follow-up visit.
- d. A 12-lead ECG will be performed before fingolimod and glatiramer acetate administration, and 6 hours after the fingolimod administration only.

e. Patients will be tested for human immunodeficiency virus, varicella zoster virus (as per guidance in Appendix 3), HSV-1, HSV-2, and rubeola virus.

g. Patients should report symptoms indicative of a relapse at a scheduled visit or at any other time and will be instructed to immediately contact the treating physician if they develop new or reoccurring or worsening neurological symptoms. A neurological examination by the independent evaluating physician must be arranged as soon as possible, preferably within 7 days of the onset of symptoms.

Table 6-2 Abbreviated schedule of assessments for patients who discontinue study drug

Period	Off-Treatment						
Visit	5	6	7/EOS				
Month	6	9	12				
Visit window (days)	±5	±5	±5				
MS relapses ^a	Х	Х	Х				
MS treatment/steroids	Х	Х	Х				
Concomitant medications	X	Х	X				
Magnetic Resonance Imaging							
EDSS			X				
TSQM			X				
		.,					
C-SSRS	X	X	X				
Physical exam	X		X				
Ophthalmologic exam ^c			X				
Dermatology examination			X				
Vital signs ^d /body weight	X	X	X				
Pulmonary function tests			X				
Laboratory values	Xe	Xe	Х				
Adverse events	X	X	X				
SAE reporting	Х	Х					

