Appendix 4: Guidance for ophthalmic monitoring

In MS studies, macular edema was reported in 0.4% of patients receiving fingolimod 0.5 mg, and the majority occurred in the first 3-4 months. Some patients presented with blurred vision or decreased visual acuity, but others were asymptomatic and diagnosed during routine ophthalmological examinations. Macular edema generally improved or resolved spontaneously after discontinuation; continuation of fingolimod in patients with macular edema has not been evaluated. Patients with diabetes mellitus or with uveitis are at increased risk of macular edema. Fingolimod has not been studied in multiple sclerosis patients with concomitant diabetes mellitus.

Ophthalmic examinations, including optical coherence tomography (OCT) and fluorescein angiography (FA), for assessment of macular edema are scheduled as outlined in Table 6-1. Similar assessments must be performed as part of an unscheduled ophthalmology visit for any patient who presents with new visual symptoms. If patients report visual disturbances at any time while on therapy, evaluation of the fundus, including the macula, should be carried out by an ophthalmologist.

Guidance on monitoring patients for possible macular edema

If macular edema is suspected during the study, an OCT must be performed as a confirmatory test. If macular edema diagnosis is confirmed on OCT, study drug must be permanently discontinued.

These patients must be followed-up with monthly ophthalmologic evaluations, including OCT, until such time as resolution is confirmed or no further improvement is expected by the ophthalmologist (based on a follow-up period of not less than three months). If the patient does not show definite signs of improvement on examination by specialist testing (e.g., OCT) after 6-8 weeks after discontinuation of study drug, then therapy for macular edema in conjunction with an ophthalmologist experienced in the management of this condition should be initiated and further managed by the ophthalmologist until either resolution of the macular edema or there is absence of any evidence of further improvement.

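### Protocol 6.5.5 ties the mandatory on-study stop for macular edema to OCT plus FA, whereas Appendix 4 requires a permanent stop on OCT alone (minor safety-text inconsistency)

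*Protocol*

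**What the plan says.** Section 6.5.5 of the protocol covers ophthalmologic examinations. Its on-study stopping rule is: "Study drug must be discontinued in any patient who has a diagnosis of macular edema confirmed by OCT and FA". The paragraph that follows sets out follow-up and times any treatment of the edema from "6 to 8 weeks after discontinuation of study drug".

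Appendix 4, under its guidance on possible macular edema, says: "If macular edema is suspected during the study, an OCT must be performed as a confirmatory test". It continues: "If macular edema diagnosis is confirmed on OCT, study drug must be permanently discontinued". The uveitis guidance in the same appendix likewise asks only for OCT when macular edema is suspected.

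Three other texts matter:

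- Screening has its own sentence in 6.5.5: "If there is a suspicion of macular edema at Screening, an OCT and FA should be performed to confirm the diagnosis".
- Table 6-1, footnote b, says: "Optical coherence tomography and fluorescein angiography will be done only if needed to confirm macular edema". The footnote to Table 6-2 and the opening of 6.5.5 say the same in substance.
- The glossary defines study drug discontinuation as "Point/time when patient permanently stops taking study drug for any reason".

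**The concern.** One mandatory safety stop has two written triggers, and the section a site would naturally consult for eye findings carries the narrower one. Because FA is done only if needed, and Appendix 4 asks only for OCT on suspicion, a site can properly hold a positive OCT and no FA. Appendix 4 then requires the stop, but the condition stated in 6.5.5 is not yet met. A site working from 6.5.5 alone could keep the patient on drug while it arranges FA, or could treat a negative FA as a reason not to stop.

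The cross-references do not settle the matter. Section 6.5.5 cites Appendix 4 only for uveitis. Section 5.5.6 cites it in a list of interruptions left to investigator judgment, not as a mandatory stop. No text says which trigger prevails.

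What is at stake is patient safety. Section 6.5.12 names macular edema as an adverse event of special interest, and Appendix 4 notes that staying on fingolimod with macular edema has not been studied.

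**Working it through.** This is a comparison of two rules; the documents state no figure to reproduce.

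**Step 1: compare the triggers for every on-study OCT/FA result.**

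| OCT | FA | 6.5.5 condition met? | Appendix 4 condition met? |
|---|---|---|---|
| Confirms | Confirms | Yes | Yes |
| Confirms | Negative | No | Yes |
| Confirms | Not done | No | Yes |
| Negative or not done | Any | No | No |

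The rules diverge only in the second and third rows.

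**Step 2: check whether the consequence differs.** Appendix 4 adds that the stop is permanent and 6.5.5 does not. Under the glossary, discontinuation is already permanent, so only the trigger differs.

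**Step 3: check whether Screening explains the 6.5.5 wording.** It does not. Screening has a separate sentence, and no study drug is being taken at that point.

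**Step 4: scale.** Inputs: 0.4% of patients on fingolimod 0.5 mg had macular edema in earlier MS studies (Appendix 4), and the final arm sizes are 352 on 0.5 mg and 370 on 0.25 mg (SAP Section 10).

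- Expected cases on 0.5 mg: 0.004 × 352 = 1.41.
- Chance of at least one case on 0.5 mg: 1 − 0.996^352 = 0.756.
- 2.5th and 97.5th percentiles of Binomial(352, 0.004): 0 and 4.
- Both fingolimod arms, assuming the same rate at 0.25 mg: 0.004 × (352 + 370) = 0.004 × 722 = 2.89.

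The documents give no rate for 0.25 mg. Section 1.1 reports a dose response for macular edema, so the equal-rate figure may be too high.

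These figures count macular edema of any kind. If f is the share of cases confirmed on OCT with FA negative or not done, the expected number of divergent cases on 0.5 mg is 1.41 × f. The documents say nothing about f, so the result lies anywhere from 0 (f = 0) to 1.41 (f = 1).

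**The case against.** The strongest reply is that the rules are nested. Section 6.5.5 gives one sufficient condition for stopping and Appendix 4 gives a broader one. Stopping on OCT satisfies both, so no precedence clause is needed. Section 5.5.6 mentions ophthalmic findings and points to Appendix 4, which has its own heading for possible macular edema, so a site handling a suspected case may well reach the stricter rule. All of this stands, and it makes the point minor. It does not remove it: the main ophthalmic section still states a narrower trigger and does not send the reader to Appendix 4 for macular edema.

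A reader might infer that 6.5.5 permits continued dosing after OCT confirmation. It does not. It is silent on that case, its follow-up text presupposes that drug has been stopped, and continuing would breach Appendix 4.

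A reader might also see a second conflict over FA, because the Appendix 4 introduction says: "Ophthalmic examinations, including optical coherence tomography (OCT) and fluorescein angiography (FA), for assessment of macular edema are scheduled as outlined in Table 6-1". That sentence defers to Table 6-1, whose footnote b limits OCT and FA to cases where confirmation is needed. The scheduling is therefore clear when the two are read together. The next sentence of the introduction, on new visual symptoms, is looser and can be read as requiring OCT and FA in symptomatic patients. Narrowing it for consistency could remove a safety test, and the documents do not show that the sponsor intends that.

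**Conclusion.** The stop rule is internally inconsistent as written, at the lowest level of severity. The triggers differ only for on-study patients confirmed on OCT with FA negative or not done. Harm would further require a site that relies on 6.5.5 alone and waits for FA.

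The number of patients is small and unknown. The 1.4 expected cases assume that the historical 0.4% applies to this arm. It is an expected count and not a ceiling, since the trial admits patients with diabetes (HbA1c up to 9%, without neuropathy) and with uveitis, both of whom Appendix 4 places at higher risk. A reader might take 1.4 as the number of patients left on drug. The documents do not support that, because it counts all macular edema and neither the divergent share nor the chance of a site departing from Appendix 4 can be estimated.

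The primary analysis and the power are unaffected. Under Section 9.4.3, patients who stop drug remain in the study and their relapses count on or off drug. SAP Section 8.6 summarizes macular edema diagnoses and lists the OCT and FA data; neither depends on which trigger applies.

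**What to change.** Replace the stop sentence in Section 6.5.5 with wording to this effect: *On study, a macular edema diagnosis confirmed by OCT requires permanent discontinuation of study drug (see Appendix 4); FA need not be obtained before stopping.*

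Leave the Screening sentence in 6.5.5 unchanged, so that OCT and FA are still used to confirm the diagnosis before randomization. Leave the Appendix 4 introduction unchanged as well.

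The cost is one sentence. It adopts the trigger that Appendix 4 already imposes, so it creates no new stopping obligation. It neither adds nor removes an assessment, and it needs no change to Table 6-1, Table 6-2 or the SAP.
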